7.2. General Methodology

Time to event methods will be used to analyze the primary objectives. The specific methods used for each analysis are given in the relevant sections within this SAP.

7.3. Center Pooling

Data from all centers will be pooled for analyzing all objectives. Adjustment for center effect will not be included in statistical modeling.

7.4. Handling of Missing Data and Dropouts

There are no plans for the imputation of any missing data. However, should the issue of missing data arise, sensitivity analyses will be conducted to assess the robustness of the primary analyses. Sensitivity

analyses include, but are not limited to tipping point analyses. Specifically for the tipping point analysis, subjects that are censored prior to the timepoint for which the survival estimate is being computed will be iteratively included as failures. For example, the earliest censored subject will be changed to a primary event (i.e., failure) at one day after their censor date. The analysis will be re-run and the estimate obtained. Then the next earliest censored subject will be changed to a primary event one day after their censor date, keeping the censored subjects already changed to primary events as primary events. The analysis will be re-run and the estimate obtained. This process will repeat until all censored subjects have been changed to primary events, such that all censored subjects will be counted as primary events in the last analysis run. Summaries of this process will be provided in order to illustrate which scenarios would and would not have resulted in success of the primary endpoint.

For subjects who are lost to follow-up, the time to event will be censored at the date the subject was last known to be free from the event when analyzing objectives with Kaplan-Meier or proportional hazards methods.

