### **12.4 Primary effectiveness objective**

The primary effectiveness objective compares the rate of chronic treatment success between study arms. Chronic treatment success is freedom from chronic treatment failure. Therefore, comparing the rate of chronic treatment success is equivalent to comparing the risk of chronic treatment failure.

Chronic treatment failure is defined as the occurrence of either

- 1) a documented episode of AF recorded on Reveal LINQ
- 2) an intervention for AF

occurring after a blanked follow-up period of 90 days from the study treatment procedure. AF episodes and repeat ablations that occur within 90 days of the study treatment procedure will not constitute chronic treatment failure.

Intervention for AF is defined as an invasive procedure intended for the definitive treatment of AF, including any ablation of the pulmonary veins or atrial triggers (other than protocol-specified ablation), interruption of AV nodal function, procedures to alter left atrial conduction or function such as the Maze procedure, or the implantation of an atrial pacemaker or atrial defibrillator; whether approved by relevant regulatory authorities or not for such indications; excluding electrical or pharmacologic cardioversion of arrhythmias and excluding procedures solely directed at the treatment of atrial flutter or atrial tachycardias.

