7.10.2.4. Analysis Methods

A log-rank test will be used to perform this hypothesis test. The log-rank test uses the time that each subject is free from chronic treatment failure, defined from the date of procedure to the date of chronic treatment failure, if it occurs, or latest of the following: a) the last follow-up visit date, or b) the last date on which AF was assessed, if chronic treatment failure does not occur during the subject's study follow-up. Subjects will be included through all available study follow-up.

In addition to the log-rank test, Kaplan-Meier curves will be used to estimate the rate of chronic treatment success. Cox proportional hazards regression will be used to estimate the hazard ratio and its 95% confidence interval between study arms.

Code similar to the following can be used for the log-rank test and Kaplan-Meier curves:

```
ODS graphics on ;
PROC LIFETEST DATA=survData conftype=loglog;
    Plots = (survival(atrisk = 0 to <end time> by <interval time>)) ;
    STRATA trtGroup;
    TIME time*event(0);
    TEST trtGroup;
RUN;
ODS graphics off ;
```

Code similar to the following can be used for the Cox proportional hazards model:

```
PROC PHREG DATA = survData;
    CLASS trtGroup;
    MODEL time*event(0) = trtGroup / TIES = efron;
RUN;
```

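### The tipping-point rule in SAP 7.4 follows one date-ordered path that ignores study arm, so it reaches the scenario most adverse to a positive result only by chance

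*SAP*

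**What the plan says.** SAP 7.4 imputes nothing in the main analysis. If data are missing, it plans sensitivity analyses and specifies one, a tipping-point analysis:

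- Scope: "subjects that are censored prior to the timepoint for which the survival estimate is being computed will be iteratively included as failures".
- First step: "the earliest censored subject will be changed to a primary event (i.e., failure) at one day after their censor date".
- Next steps: "Then the next earliest censored subject will be changed to a primary event one day after their censor date", with earlier conversions kept and the analysis repeated each time.
- End: the process runs on, "such that all censored subjects will be counted as primary events in the last analysis run".
- Output: summaries meant to "illustrate which scenarios would and would not have resulted in success of the primary endpoint".

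No step mentions study arm, and nothing is said about the first 90 days. The section adds that sensitivity "analyses include, but are not limited to tipping point analyses", but neither it nor Protocol 12.10 describes another one.

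Two other provisions bear on the rule. Protocol 12.4, repeated in SAP 7.10.2.3, says that "AF episodes and repeat ablations that occur within 90 days of the study treatment procedure will not constitute chronic treatment failure". For the primary log-rank test, SAP 7.10.2.4 says: "Subjects will be included through all available study follow-up".

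**The concern.** The primary effectiveness test compares two arms. Failing dropouts in both arms partly cancels, and a Control conversion can make the result stronger. The state that puts a positive result under most strain is the one-sided one: Treatment dropouts fail, Control dropouts stay censored. A single path ordered by censoring date does not aim at that state.

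Dropout related to arm is plausible here, because subjects and center staff are blinded only until the pulmonary vein isolation is done (Protocol 6.9, SAP 5.3). With about 41 events planned, a few Treatment dropouts can decide the result. This is the only sensitivity analysis spelled out, so a reader of the final report would take a path that never tips as evidence of robustness.

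There are two further defects of wording. A subject censored on day 40 would fail on day 41, which the endpoint definition does not allow. And the scope clause depends on a timepoint that a log-rank test over all follow-up does not have.

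**Working it through.** **Inputs.** From SAP section 6 and its EaST output: 1:1 allocation, success at 6 months of 50% (Control) and 75% (Treatment), 16 months of accrual, 22 months in total, dropout of 5% per 6 months for planning and about 1% expected, 25 + 16 = 41 events, 2 Control and 3 Treatment dropouts, and a final boundary of Z = 2.049 (two-sided p about 0.0405; SAP 7.8 rounds to 0.04). The 10% attrition rate used below is an assumption and is not in the documents.

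**1. The plan's own figure.** HR = ln 0.75 / ln 0.50 = 0.415. The drift per root event is |ln 0.415| / 2. With looks at 14, 19 and 41 events and boundaries 2.576, 2.611 and 2.049, simulation gives 17.6% + 10.1% + 50.9% = 78.6%, which matches SAP Table 1. An exponential model with 35 per arm gives 25.9 + 15.8 events and 1.9 + 2.8 dropouts, close to the SAP's counts.

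**2. How often the path meets the adverse state.** With 3 Treatment and 2 Control dropouts, it does so only if all three Treatment dropouts are censored first. Under random order the probability is 1 / C(5,2) = 1/10 = 10%.

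**3. One simulated trial.** It had 25 v 16 events and p = 0.0113. Dropouts occurred on days 90 (Control), 120 (Treatment), 120 (Treatment), 289 (Control) and 332 (Treatment). The SAP path gives p = 0.0078, 0.0136, 0.0223, 0.0139 and 0.0188: both Control conversions lower p, and the path never tips. Failing the three Treatment dropouts alone gives p = 0.0408, just past the final boundary. All three left after day 90, so the contrast comes from arm and not from blanking.

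**4. How often this happens.** 8,000 trials per setting: 35 per arm, 16-month accrual, 22-month study, non-informative dropout, significance at Z <= -2.049. Only dropouts were converted. The SAP path was required to stay significant at every step. Treatment-only failures were dated no earlier than day 91.

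| Attrition per 6 months | Event model | Never tips on SAP path | Survives Treatment-only failure | SAP path never tips, Treatment-only does |
|---|---|---|---|---|
| 1% (expected) | constant hazard from day 0 | 97.0% | 96.6% | 0.5% |
| 1% | no events before day 90 | 98.0% | 97.7% | 0.3% |
| 5% (planning) | constant hazard from day 0 | 88.1% | 82.0% | 6.5% |
| 5% | no events before day 90 | 91.9% | 87.0% | 4.9% |
| 10% (assumed) | constant hazard from day 0 | 77.7% | 61.4% | 16.4% |
| 10% | no events before day 90 | 84.2% | 68.8% | 15.4% |

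Percentages are of significant trials. With the 51-month enrollment now expected (Protocol 1.2, SAP 5.1) and no events before month 3, two runs of 1,500 and 6,000 trials gave 3.8% and 4.8% in the last column at 5% attrition, and 16% and 14.9% at 10%.

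**5. Blanking.** At 5% attrition about 1.6 to 1.7 of the 4.6 to 4.7 dropouts per significant trial fall in the first 90 days. Moving imputed Treatment failures there to day 91 changes the share still significant from 79.4% to 80.3% (constant hazard) or from 85.8% to 86.0% (no events before day 90), so by 1 point or less.

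**6. Study-end censoring.** The timepoint clause fits a Kaplan-Meier estimate at a fixed time, such as the 6-month safety estimate. But success is defined only for the effectiveness objective, since SAP 7.10.1.2 sets no performance requirement for safety. If subjects censored at study end are also converted, the share of significant results that survive the last run falls from 94% to 82.5% (16-month accrual, no events before day 90, 5% attrition, 2,000 trials), and with 51-month accrual from 95% to 92%. Two programmers could therefore report different answers from the same text.

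**The case against.** The case against giving this much weight is good, and most of it stands on size.

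- SAP 7.4 has no threshold for robustness, and the tipping-point output does not enter the pass/fail rule in SAP 7.8. A reader might infer that the rule certifies fragile results as robust. The documents do not support that: they promise a descriptive summary and leave room for other analyses.
- A reader might also infer that the adverse scenario is never examined. The path can pass through it, so the accurate statement is that it is not examined systematically.
- If only the last run is compared with Treatment-only failure, the gap looks larger: with 51-month accrual, 95% v 88-89% at 5% attrition and 90% v 70-71% at 10%, which suggests 6% to 20%. But the SAP repeats the analysis after every conversion, so tipping at any step shows. The table in the working is the fair comparison.
- The path is not toothless. At 5% attrition it tips about 8% to 12% of significant results (100 - 91.9 and 100 - 88.1).
- The simulated trials have a true benefit and non-informative dropout. A result that fails the one-sided stress test is not thereby wrong.
- The study is a feasibility study, and the SAP says its estimates serve the pivotal design whether or not the test is significant.
- The timepoint clause can be read as already excluding study-end censoring.

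The objection does not remove the defect in design. The one analysis specified leaves its most informative comparison to the order in which dropouts happen to be censored, conflicts with the endpoint definition, and is open to two readings.

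**Conclusion.** The point holds as a modest but real weakness. The rule does not systematically test the scenario in which Treatment dropouts fail and Control dropouts stay censored. Its summary can overstate robustness in about 4-7% of significant results at the planning attrition of 5%, under 1% at the expected 1%, and about 15-16% at an assumed 10%. It becomes material only if attrition runs well above expectation. The blanking conflict is one of definition, with little numerical effect. The undefined timepoint matters more for reproducibility.

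These sizes assume the design effect, constant hazards (from day 0 or from day 90), non-informative dropout, the final boundary only, and conversion of dropouts only. Against the 0.05 still stated in SAP 7.10.2.2, the example in the working would not tip. Dropout that depends on arm or outcome was not simulated.

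**What to change.** Rewrite the tipping-point paragraph of SAP 7.4 before unblinded results are used:

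1. Vary the number of converted dropouts separately by arm, from none to all in Treatment by none to all in Control. With 3 and 2 dropouts the grid has 4 x 3 = 12 cells, of which the present path visits 6. State the order of conversion within each arm.
2. Report explicitly the row in which Treatment dropouts fail and all Control dropouts stay censored.
3. Date each imputed effectiveness failure at the later of day 91 and the day after censoring.
4. State that subjects censored administratively at study end stay censored, and replace the reference to a timepoint for the log-rank test.

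The cost is a paragraph of SAP text and a short extra program. The robustness statement may come out less favorable. Nothing is lost: apart from the day-91 dating, the present path remains one route through the grid.

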7.5. Adjustments for Multiple Comparisons

No alpha level adjustment for multiple comparisons will be made given the feasibility nature of this study.

7.6. Demographic and Other Baseline Characteristics

Information summarizing patient characteristics at baseline will be presented using descriptive statistics and tables for the mITT analysis set. Variables presented may include, but are not limited to, demographics, medical history, physical examination, NYHA classification, office blood pressure, arrhythmic symptoms, medications, and lab test results.

For quantitative variables, the mean, standard deviation, median, first quartile and third quartiles, minimum, and maximum will be presented based on non-missing values. For qualitative variables, counts and percentages will be given, using subjects with non-missing data as the denominator. The number of missing and non-missing values for each variable will be included.

The summary tables will include a column for mITT treatment arm subjects, mITT control arm subjects, and all mITT subjects.

Age will be computed using the variables AGE_YEARS and AGE_MONTH from the Baseline CRF: Age = AGE_YEARS + AGE_MONTHS/12

7.7. Treatment Characteristics

Procedural measure comparisons between study arms will be done in ancillary objective 3 (Section 7.10.6).

7.8. Interim Analyses

Two interim analyses are planned for the study. These analyses would be performed after 32 and 50 subjects have been randomized and completed their 6-month follow-up visits, respectively. Both the

sponsor and the DMC will assess the results of the interim analyses of the primary effectiveness objective and based on this assessment, the sponsor may decide to stop enrollment. However, while there are formally defined stopping rules for a successful primary effectiveness endpoint, there are no stopping rules for futility.

Patients randomized to the trial who have not reached 6-months of follow-up are not considered in assessing the primary effectiveness objective.

The time points of the analyses and criteria for study success are given in Table 1 below:

Table 2: Timing and Success Criteria for Interim and Final analyses

Time Point of Interim Analyses of the Primary Effectiveness Objective	Cumulative Alpha	Boundary*	Pass/Fail Primary Effectiveness Objective
After 32 subjects were randomized and completed their 6-month visit	0.01	0.01	If a two-sided p-value ≤ 0.01 , in favor of the treatment group, then the study passed the primary effectiveness objective
After 50 subjects were randomized and completed their 6-month visit	0.015	0.008	If a two-sided p-value ≤ 0.008 , in favor of the treatment group, then the study passed the primary effectiveness objective
Final Analysis: After 70 subjects were randomized and completed their 6-month visit	0.05	0.04	If a two-sided p-value ≤ 0.04 , in favor of the treatment group, then the study passed the primary effectiveness objective

*Boundaries were calculated using EaST 6.4.1, using the Survival Module.

In addition to reviewing the effectiveness data from the interim analyses, the DMC will be responsible for assessing the accumulating data on safety of the procedures during the study. The primary responsibility of the DMC is to safeguard the interests of study participants. The DMC also monitors the overall conduct of the clinical study. Further information regarding the DMC is found in Appendix C: Data Monitoring Committee.

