#### **12.4.5 Determination of Patients/Data for Analysis**

All randomized subjects in the modified intention-to-treat cohort will be included in the analysis.

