The original sample size calculation was performed in PASS 2008 using the log-rank (Lakatos) procedure. Updates to incorporate interim analyses were performed using EaST, version 6.4.1 with the survival module. Accounting for a study attrition rate of up to 5% per 6 months ensures that the study will maintain the planned power of 78% in case attrition is higher than expected (approximately 1% per 6 months).

A summary of the EaST output detailing the analyses is given on the following page.

Design: Survival Endpoint: Two-Sample Test - Parallel Design - Logrank Given Accrual Duration and Study Duration

Test Parameters	
Design ID	Des3
Design Type	Superiority
Number of Looks	3
Test Type	2-Sided
Specified α	0.05
Power	0.786
Model Parameters	
HR = λ_c/λ_e	
Under H0	1
Under H1	0.415
Ratio of % Surv. at Period #1:	1.5
Cum. % Surv. by Time =	6
Control (S_c)	50
Treatment (S_e)	75
Var (Log HR)	Null
Allocation Ratio (n_e/n_c)	1
Boundary Parameters	
Spacing of Looks	Unequal
Efficacy Boundary	Interp.
Accrual / Dropouts Parameters	
Cum % Accrued	100
Accrual Duration	16
Max Study Duration	22
Dropout	Yes

Variable Follow-Up Design: All subjects are followed until failure, drop out or end of study.

Sample sizes and events have been rounded.

Sample Size Information

	Control Arm	Treatment Arm	Total
Sample Size (n)			
Maximum	34	35	69
Expected H1	31.666	31.666	63.331
Expected H0	34.288	34.288	68.577
Events (s)			
Maximum	25	16	41
Expected H1	22.52	13.022	34.031
Expected H0	20.325	20.325	40.62
Dropouts (d)			
Maximum	2	3	5
Expected H1	1.723	2.547	4.27
Expected H0	1.985	1.985	3.97
Maximum Information (I):			10.25

Accrual and Study Duration

	Accrual Duration	Study Duration
Maximum	16	21.998
Expected H1	14.686	19.024
Expected H0	15.902	17.361

Stopping Boundaries: Look by Look

Look #	Info. Fraction (s/s_max)	Events (s)	Cumulative α Spent	Boundaries
Efficacy Z				
Upper		Lower		
1	0.341	14	0.01	2.576 -2.576
2	0.463	19	0.015	2.611 -2.611
3	1	41	0.05	2.049 -2.049

Events, Sample Size, Dropouts, Pipeline and Analysis Times: Look by Look (Under H0)

Look #	Info. Fraction (s/s_max)	Sample Size (n)	Events (s)	Dropouts (d)	Pipeline (n-s-d)	Analysis Time	Boundary Crossing Prob (Incremental)
Efficacy							
Upper		Lower					
1	0.341	39	14	2	23	8.863	0.005
2	0.463	46	19	2	25	10.639	0.003
3	1	69	41	4	24	17.481	0.017

Events, Sample Size, Dropouts, Pipeline and Analysis Times: Look by Look (Under H1)

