Look #	Info. Fraction (s/s_max)	Sample Size (n)	Events (s)	Dropouts (d)	Pipeline (n-s-d)	Analysis Time	Boundary Crossing Prob (Incremental)
Efficacy							
Upper		Lower					
1	0.341	46	14	2	30	10.492	1.216E-5
2	0.463	55	19	3	33	12.575	1.846E-6
3	1	69	41	5	23	21.998	5.177E-7

Dropout Information : Prob. of Dropout

Period #	By Time	Control	Treatment
1	6	0.05	0.05
2	12	0.1	0.1
3	18	0.15	0.15
4	22	0.183	0.183

7. Statistical Methods

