7.1.3. Analysis Sets

Cut-off dates will be applied to the study data when creating snapshots for study reporting. The analysis sets will be created from the applicable snapshot (e.g., for final report).

Enrolled

Patients who signed informed consent and met inclusion/exclusion criteria. Deviations and adverse events will be reported for all enrolled subjects. Enrolled subjects will be included in the CONSORT flow diagram.

Randomized

Enrolled subjects who are randomized.

Modified intent-to-treat

A modified intention-to-treat (mITT) analysis will be performed for the primary objectives. The mITT analysis set will include all randomized subjects that undergo a pulmonary vein isolation procedure (i.e. have a cryocatheter inserted). Patients that are randomized, but exit the study without undergoing a pulmonary vein isolation procedure will not be included in the mITT analysis set. Patients that are randomized to the treatment arm, but do not have the renal denervation procedure, will not be included in the mITT analysis set.

This analysis set is used for the following objectives described previously in Section 4:

- Primary safety

- Primary effectiveness
- Ancillary Objective 1
- Ancillary Objective 2
- Ancillary Objective 3
- Ancillary Objective 4
- Ancillary Objective 6

Secondary Objective

All subjects in the mITT cohort (i.e. subjects used for the Primary Effectiveness Objective) that do not undergo an additional pulmonary vein ablation procedure during the 90 day blanked follow-up period will be included the analysis of the secondary objective.

Ancillary Objective 5

The following subjects will be included in the analysis of ancillary objective 5:

- All subjects in the mITT cohort (i.e. subjects used for the Primary Effectiveness Objective) that do not undergo an additional pulmonary vein ablation procedure during the 90 day blanked follow-up period will be included this analysis

AND

- Have not used Class I and III anti-arrhythmic drugs following the blanking period

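### SAP 7.8 leaves randomised subjects with under 6 months of follow-up out of the interim effectiveness test, in conflict with the mITT set, the censored log-rank test and the powered design; the loss of information is small

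*SAP*

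**What the plan says.** SAP 7.8 times the two interim looks by the number of subjects with a completed 6-month visit (32, then 50), and adds: "Patients randomized to the trial who have not reached 6-months of follow-up are not considered in assessing the primary effectiveness objective". Protocol 12.8 uses the same two counts for timing but has no exclusion of this kind.

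The other governing text points the other way:

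- SAP 7.10.2.4 (and Protocol 12.4.4) specifies a log-rank test with censoring at the later of the last visit or the last AF assessment: "Subjects will be included through all available study follow-up".
- Protocol 12.4.5: "All randomized subjects in the modified intention-to-treat cohort will be included in the analysis". SAP 7.10.2.5 likewise uses the mITT set.
- SAP 7.1.3 defines that set with no minimum follow-up: "The mITT analysis set will include all randomized subjects that undergo a pulmonary vein isolation procedure (i.e. have a cryocatheter inserted").
- SAP 7.4 censors losses rather than removing them: "For subjects who are lost to follow-up, the time to event will be censored at the date the subject was last known to be" event-free.
- The EaST output in SAP section 6 describes the powered design: "Variable Follow-Up Design: All subjects are followed until failure, drop out or end of study".

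Chronic treatment failure counts from day 90 (Protocol 12.4, SAP 7.10.2.3), so a subject between day 90 and month 6 can already have a valid primary event.

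**The concern.** A log-rank test needs no minimum follow-up, because a recently treated subject contributes the time observed and is then censored. Deleting such subjects throws away events that meet the endpoint definition. It also makes the interim data set differ from the one on which the boundaries and power were computed.

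Each look carries a pass/fail p-value, and the sponsor may stop enrolment on it. Two programmers could follow the SAP, one by 7.8 and the other by 7.1.3 with 7.10.2.4, and reach different p-values.

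The SAP also does not define when 6 months of follow-up has been reached. If the timing trigger (a completed 6-month visit) were used as the inclusion test, subjects who died, withdrew or were lost before that visit would vanish from the look. That would be selection on post-randomisation experience.

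**Working it through.** **Inputs.** From SAP section 6: 1:1 allocation; 50% v 75% success at 6 months; dropout of 5% per 6 months; uniform accrual over 16 months; looks at 14, 19 and 41 events; Z boundaries 2.576, 2.611 and 2.049. From SAP 5.1 and Protocol 1.2: about 51 months of enrolment now expected. From SAP 7.10.2.3: 90-day blanking, taken as B = 3 months.

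**Formulas.**
- HR = ln 0.75 / ln 0.50 = 0.415, so |ln HR| = 0.879.
- Failure hazard per arm λ = −ln(S)/(6 − B), with B = 0 or 3; dropout hazard δ = −ln(0.95)/6.
- Probability of an observed failure by follow-up f > B: e^(−δB) · λ/(λ+δ) · [1 − e^(−(λ+δ)(f−B))].
- Expected events at calendar month t: this probability integrated over entry times, for all accrued subjects or only for those entered by t − 6.
- First-look crossing probability with d events: 1 − Φ(2.576 − 0.879·√(d/4)).

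**Reproducing the plan.** With 14 events, 0.879·√(14/4) = 1.645 and 1 − Φ(0.931) = 17.6%, the SAP Table 1 figure. The three-look calculation gives 17.6% + 10.1% + 50.9% = 78.6%. With 69 subjects over 16 months and B = 0, expected events at months 10.492, 12.575 and 21.998 are 14.0, 19.0 and 41.0, matching EaST.

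**Who supplies the planned events.** The EaST rows under H1 read "1 0.341 46 14 2 30 10.492 1.216E-5" and "2 0.463 55 19 3 33 12.575 1.846E-6". The first has 46 subjects, 14 events, 2 dropouts and 30 in the pipeline.
- At month 10.492 only about 19.4 of 45.3 accrued subjects have 6 months of potential follow-up. They supply 8.8 of the 14.0 events.
- At month 12.575 it is 28.4 of 54.2 subjects and 13.8 of 19.0 events.

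So the powered looks rely on subjects that 7.8 removes. SAP Table 1 labels the looks as 32 and 50 patients with six-month follow-up, but its power figures belong to 14 and 19 events among all accrued.

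**Effect of the sentence at the actual triggers.** With 70 subjects and accrual A months, k subjects reach 6 months at t = 6 + kA/70. Losses are computed before rounding.

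| Accrual, blanking | Look (month) | Subjects: all / ≥6 months | Events: all / ≥6 months | Lost |
|---|---|---|---|---|
| 16 months, none | 1 (13.3) | 58.3 / 32 | 21.2 / 15.9 | 5.3 |
| 16 months, none | 2 (17.4) | 70 / 50 | 32.4 / 27.4 | 4.9 |
| 16 months, 90 days | 1 (13.3) | 58.3 / 32 | 21.2 / 18.6 | 2.6 |
| 16 months, 90 days | 2 (17.4) | 70 / 50 | 35.0 / 32.4 | 2.6 |
| 51 months, none | 1 (29.3) | 40.2 / 32 | 22.4 / 20.8 | 1.7 |
| 51 months, none | 2 (42.4) | 58.2 / 50 | 37.3 / 35.7 | 1.7 |
| 51 months, 90 days | 1 (29.3) | 40.2 / 32 | 24.9 / 24.1 | 0.8 |
| 51 months, 90 days | 2 (42.4) | 58.2 / 50 | 41.2 / 40.4 | 0.8 |

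First-look crossing probability, all v restricted:
- 16 months, no blanking: 29% v 20.5%
- 51 months, no blanking: 31.1% v 28.4%
- 51 months, 90-day blanking: about 35% v 34%

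**Overall operating characteristics (16 months, no blanking, the worst row).** By formula, power is 79.3% restricted v 79.2% all data, and two-sided type I error is 0.0485 v 0.0462. A simulation of 6,000 log-rank trials gives power of 77.8% v 78.0%. Simulated type I error across the scenarios was 0.048 to 0.059, with no clear difference between the rules (standard error about 0.003).

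**The case against.** The strongest reply is that little is at stake. The larger losses need both 16-month accrual and failures from day 0. The documents expect about 51 months of enrolment and count no failure before day 90, so the realistic loss is under one event per look. Even in the worst row the restricted looks hold 15.9 and 27.4 events, above the planned 14 and 19. A reader might infer that the sentence leaves the interims short of planned power or distorts the error rate, but the figures do not support that.

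The two rules can also be read together: 7.10.2.4 says how much follow-up an included subject contributes, and 7.8 says who enters a look. If 6 months means time since procedure, the cut is administrative and unrelated to arm or outcome, and at the final look all 70 subjects meet it.

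A reader might also infer that subjects who have failed are deleted because they never reach the visit. Failure is not among the exit reasons in Protocol 6.24, and randomised subjects are to be followed to study closure. A subject who fails at month 4 would ordinarily still reach month 6.

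All of this stands as to size. It does not remove the inconsistency. The mITT definition and Protocol 12.4.5 say who is analysed and set no follow-up minimum, Protocol 12.8 has no exclusion, and the EaST looks count everyone accrued. The sentence might have been meant only to define the trigger count, but it does not say so, and that intent would need the same edit.

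**Conclusion.** The point holds as an inconsistency that should be corrected, with a small cost in interim information. Under 51-month enrolment and 90-day blanking it discards about 0.8 of 24.9 events at look 1 and 0.8 of 41.2 at look 2. The upper end, about 5 events per look, applies only with 16-month accrual and no blanking.

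On the time-since-procedure reading, overall power, the planned 17.6% at look 1, type I error and the final analysis are essentially untouched. On the completed-visit reading, early exits could be dropped from a look, contrary to SAP 7.4. The SAP does not settle which reading applies, so that consequence is conditional.

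The figures assume exponential failure and dropout, uniform accrual, the SAP's 50% v 75% effect and, with blanking, all failure hazard falling between day 90 and month 6 at a rate that still gives those 6-month success rates.

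**What to change.** Replace the sentence in SAP 7.8 with:

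*The 32- and 50-subject counts set only the timing of each look; each interim analysis includes all mITT subjects with a procedure date on or before the data cut-off, with event and censoring times as defined in 7.10.2.4.*

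Keeping the 7.10.2.4 rule matters. Censoring on LINQ data alone would depart from the final analysis and would not cover interventions for AF, which are part of the endpoint.

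Add that each boundary is computed from the observed event count using the planned cumulative alpha (0.01, 0.015, 0.05). Event counts at the 32- and 50-subject triggers are expected to exceed 14 and 19 under either rule, and including everyone moves them slightly further. The fixed p-value thresholds in SAP Table 2 and Protocol 12.8 should then be marked as planning values.

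The cost is minor. SAP 7.1.3 already provides for cut-off snapshots, so no new data are needed. The boundaries must be recalculated at each look, and the interim data set will include some less mature follow-up.
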